Study Title: A Novel smartphone-based intervention to support smoking cessation and adherence to antiretroviral therapy among people living with HIV: A pilot randomized clinical trial

UM IRB Study Number: 20190181

Clinical Trials Registration #: NCT03999411

Date: 06/29/2020

Clinical Trials Registration #: NCT03999411

Date: 6/29/20

1) Protocol Title

A Novel smartphone-based intervention to support smoking cessation and adherence to antiretroviral therapy among people living with HIV: A pilot randomized clinical trial

2) Objectives*

Our proposed study aims to:

- 1. We will conduct 3-arm pilot randomized controlled trial (RCT) to test the feasibility, acceptability, and potential efficacy of a combined intervention consisting of an evidence-based MT smoking cessation app "*Crave-to-Quit*" with vDOT app "*emocha*" to improve ART adherence among PLWHIV smokers; and
- 2. We will conduct a post-intervention process evaluation consisting of semistructured interviews with select participants to fine-tune the intervention based on feedback from participants for further testing in Phase II large-scale RCT.

Findings will inform a larger study of the effectiveness of cessation approaches with great potential for translation and dissemination to PLWHIV smokers throughout the US.

3) Background*

PLWHIV are at high risk for tobacco-related health disparities. Smoking prevalence in PLWHIV is triple that of the general population (47% - 65% vs. 17%, respectively). ¹⁻⁴ Most PLWHIV smokers are members of marginalized groups (e.g., ethnic minorities, migrants, men who have sex with men), ⁴ unemployed, and have low social support. ⁵ Compared to nonsmokers, PLWHIV smokers have threefold the risk of cancers, ⁶ double the risk of cardiovascular complications, ⁷ a 6 to 15 years shorter lifespan, ⁸ and lower self-reported quality of life. ⁹ In contrast, smoking cessation among PLWHIV reduces the risk of cardiovascular disease by 20%, non-AIDS malignancy by 34%, and overall mortality by 16%. ¹⁰ There is also an unmet need to develop innovative smoking cessation interventions for PLWHIV that can: 1) increase their access to treatment, 2) address their unique psychosocial profile, and 3) address the intersection between smoking and adherence to ART.

Two systematic reviews conclude that *Smartphone-based Smoking Cessation Applications (Apps)* are effective and significantly increase access to treatment. ^{19,20} In addition to their high potential for dissemination, smartphone apps provide a promising

Clinical Trials Registration #: NCT03999411

Date: 6/29/20

medium to deliver an intervention due to their availability, relatively low cost, and ease of use. Compared to in-person treatment, this approach can be standardized, reduce stigma associated with seeking treatment, allow the use of multiple methods to deliver the intervention (e.g., video, audio), facilitate the integration of the treatment into user's daily life, help tracking user's progress 24/7, and simultaneously boosting user's engagement, a strong predictor of smoking cessation. ²¹⁻²⁴

Depression and craving are two major predictors of smoking relapse in PLWHIV.²⁸ Depression among PLWHIV is up to three times higher than that in the general population.^{29,30} In addition, smoking cessation is a major life stressor and is strongly linked with psychological stress, depression, and negative and positive affect that can lead to relapse.^{31,32} One promising strategy for smoking cessation in PLWHIV is *Mindfulness Training* (MT). MT proved to be effective in reducing both self-report and objective indices of negative affect and psychological stress.^{33,34} MT also can help smokers control craving by being less emotionally reactive and less prone to relapse related to avoidance of distressing symptoms.³⁵ In PLWHIV, MT was feasible and effective at improving quality of life, aging, emotional well-being, immunological status, and coping with HIV.³⁸ Yet, MT for smoking cessation in this population has not been implemented or tested.

Based on the social cognitive theory, self-monitoring is a key component of selfmanagement because it gives patients insight into the dynamic relationship between triggers and the target behavior at the time and in the context in which they occur.³⁹ Tracking ART intake while quitting smoking can help individuals self-monitor their compliance to treatment, identify triggers to noncompliance, and ultimately improve their adherence to treatment. Video Directly Observed Therapy (vDOT) of patients taking their medications has become a cornerstone to improve adherence to treatment in several diseases (e.g., tuberculosis). Emocha Mobile Health Inc. has recently developed an app "emocha" that uses vDOT following the CDC protocol to improve medication adherence. 40 Several studies have shown that "emocha" can secure medication adherence rates of 90-95%. 41,42 Recently, [name] developed an evidence-based mindfulness smoking cessation app "Crave-to-Quit" adapted from an in-person MT relapse prevention smoking cessation intervention that proved to be effective in the general population. 43-47 Building on his work, and using a mixed-method approach of quantitative and qualitative research, we propose to: 1) test the feasibility, acceptability, and potential efficacy of a combined intervention consisting of an evidence-based MT smoking cessation app "Crave-to-Quit" with vDOT app "emocha" to improve ART adherence in a pilot randomized clinical trial (RCT) among PLWHIV smokers; and 2) fine-tune the intervention based on feedback from participants for further testing in Phase II large-scale RCT.

4) Inclusion and Exclusion Criteria*

Those eligible for inclusion area those who:

Clinical Trials Registration #: NCT03999411

Date: 6/29/20

- \geq 18 years old,
- have been prescribed ART medication in the prior 6 months
- have smoked ≥ 5 cigarettes/day in the past year
- be interested in making a quit attempt in the next 30 days
- own a smartphone (apple/android), and plan to keep it active for the next 3 months
- read/speak English
- be able to provide consent
- have no plans to move in the next 3 months
- not pregnant or planning to be pregnant in the following 3 months

We will not include any of the following groups:

- Adults unable to consent
- Individuals who are not yet adults (infants, children, teenagers)
- Pregnant women
- Prisoners
- Have contraindication to NRT (past month myocardial infarction, history of serious arrhythmias/or unstable angina pectoris, dermatological disorder),⁶³
- Currently being treated for a psychiatric condition.
- Currently being treated for smoking cessation, alcoholism, or illicit drug use

5) Procedures Involved*

Aim 1: The Clinical Trial

We will be provided with a list of potentially eligible participants including their names, contact information, smoking status, most recent HIV-1 viral load (VL), CD4 count, ART regimen history (e.g., time since first starting ART, current prescription) from the UM HIV Registry (pls. see LOS from [name]; their IRB # is pending approval of this protocol). This will include HIV Registry participants who have previously given consent to be contacted for future research studies. Eligible participants will be contacted by phone and invited to participate in the study. Those who are interested will be screened. Those who are eligible will be scheduled to attend the orientation session. Those who are not eligible, or decline to participate will be encouraged to quit smoking and given a list of available resources. We will additionally recruit participants at HIV community health centers in Miami. The process here will be the same, where interested participants will be screened for eligibility and scheduled for an orientation session.

Breath carbon monoxide (CO) (for cotinine analysis) will be collected at baseline for participants to confirm their smoking status. The breath sample will be collected with a portable CO monitor (Micro COTM by Micro Direct, Inc.). Cut-offs of < 8 ppm for CO

Clinical Trials Registration #: NCT03999411

Date: 6/29/20

and <10 ng/ml for cotinine will be used to determine smoking status (Benowitz et al 2002).

Participants will be assigned to blocks, based on gender. Then, within each block, participants will be randomly assigned to one of three treatment arms:

- 1. Usual Care (UC)/control: Participants in this group will receive a brief advice to adhere to ART, a brief advice to quit smoking, 6-week supplies of NRT, and self-help materials to quit smoking and adhere to ART.
- 2. Only smoking cessation intervention (*Crave-to-Quit* app): This intervention is based on the theory of mindfulness-based cognitive therapy (MBCT) for relapse prevention.⁶⁴ The MBCT uses cognitive behavioral therapy methods in collaboration with MT techniques. Cognitive methods focuses on the development of personal coping strategies that target solving problems and changing unhelpful patterns in cognitions (e.g. thoughts, beliefs), behaviors, and emotional regulation.⁶⁵ MT focus on becoming aware of all incoming thoughts and feelings and accepting them, but not attaching or reacting to them.³⁶ This process is known as "Decentering" and aids in disengaging from self-criticism and rumination that can arise when reacting to negative thinking patterns.⁶⁶ Participants in this group will receive the UC for adherence to ART, one in-person orientation sessions, 6-week supplies of NRT, the "*Crave-to-Quit*" app, and two brief follow-up phone calls.

Orientation session. This session will occur 3 weeks before quit date and will last for 90 min. During the session, a research associate will explain the purpose, format, and procedures of the study. Participants will then watch a video that explains the specifics of their respective arm's study activities; there will be a different video for each of the 3 arms. After the video the research associate will go through the written informed consent, have the participant sign, and have the participant complete the baseline assessment. Then, participants will be instructed to download on their phone the "Crave-to-Quit" app and will receive a tutorial explaining the app content and features to troubleshoot any issues, followed by training on how to use the app and to practice MT techniques introduced in the app. Participants will be instructed to start using the app, and the app will assign a quit date within the next 3 weeks. Participants will receive 6 weeks of NRT, and will be instructed to start using the NRT at the quit date. Orientations and collection of consent may be conducted individually or in groups, according to participants' schedules.

The Crave-to-Quit app. The app is comprised of 22 modules for 22 days, 5–15 minutes each, designed to teach MT using audio, video, and animation.⁴⁴ Participants have access to only one new module per day, and subsequent days are locked to prevent skipping ahead (pls. see LOS from [name] from MindSciences). The app teaches three basic formal MT techniques including *Body Scan* (bringing awareness to different parts of the

Clinical Trials Registration #: NCT03999411

Date: 6/29/20

body to foster awareness of body sensations that constitute cravings and affective states), *Loving-Kindness* (repeating phrases such as "may X be happy" to foster acceptance of oneself and others), *Breath Awareness* (paying attention to the breath wherever one feels it most strongly in the body to help retrain the mind away from habitually engaging in self-related thinking toward a more present-centered awareness), and one informal MT RAIN (Recognize, Accept, Investigate, and Note what cravings feel like as they arise/pass away). In RAIN, participants are asked to identify their smoking trigger, rate their craving, and choose between using RAIN to ride out their craving, or completing an audio-guided exercise to 'smoke mindfully' by paying attention to the moment-to-moment experience and bodily sensations of smoking. The app also includes other features such as social support (quit friend sign-ups, the tip of the week), activity feed (to track interaction with the app), and my morning stats (to track smoking).

Two brief follow-up phone calls. The first phone call will occur one day before the quit date to remind participants about their quit date and provide support. The second will occur at the end of treatment (6 weeks after quit date) to review progress, provide support, and schedule the 3-month follow-up visit.

3. The combined intervention (Crave-to-Quit + emocha apps): In addition to the intervention in the second group, participants in this group will be instructed during the *Orientation Session* to download on their phone the *emocha app* and will receive a tutorial explaining the app content and features. The study team will explain to participants that the app will help them in tracking dose-by-dose medication adherence by recording a video for themselves taking their medication. Participants will be instructed to find a private place to take their medication, make sure their face is well lit when recording, have a clear glass of water, state their name, the date, and each medication as they take it, display their medication pills, show medication in the mouth before swallowing, drink water, show open mouth after swallowing, and repeat the same procedure every time they take the medication. During the 3-month trial, our staff will have full access to the app's web portal to navigate and collect information about patients' adherence to ART (pls. see LOS from emocha Mobile Health Inc.).

At the orientation session, participants will complete a baseline assessment consisting of:

- Demographics and HIV history. Age, race/ethnicity, sexual orientation, relationship status, education, employment, income, time since HIV diagnosis, and HIV 1 RNA VL (from medical chart), ART regimen history, time since first starting ART, current ART prescription, 72 VAS for adherence to ART. 61,62
- *Smoking*. Smoking history, past quit attempt, motivation to quit, confidence in quitting, Fagerström test for nicotine dependence, 73 12-item smoking self-efficacy to resist urge to smoke, 74 and 15-item Minnesota nicotine withdrawal scale (i.e., craving, irritability, anxiety, depression). 75

Clinical Trials Registration #: NCT03999411

Date: 6/29/20

Mindfulness skills: The five facet MT questionnaire that measures MT skills related to observing, describing, acting with awareness, non-judging of inner experience, and non-reactivity to inner experience.⁷⁶

• Others. The 10-item Centers for the Epidemiologic Study of Depression (CES-D) scale, 77 social support, 78 quality of life, 79 and alcohol and substance use (ASSIST). 80

Participants will receive \$50 for completing the baseline assessment.

All participants will receive one in-person follow-up assessment at 3 months after enrollment to assess their smoking status and adherence to ART as well as get information about concomitant smoking and NRT use, use of additional NRT or cessation drugs (e.g., bupropion), and use of other tobacco methods. Breath CO (for cotinine analysis) will be collected at the 3-month follow-up points for participants who report abstinence. The breath sample will be collected with a portable CO monitor (Micro COTM by Micro Direct, Inc.). Cut-offs of 8 ppm for CO and 10 ng/ml for cotinine will be used to determine abstinence (Benowitz et al 2002).

The following will be assessed at the three-month intervention:

- All baseline assessments except demographics.
- *Usability and engagement*. The absolute number of times logged into the apps will be calculated for each user to obtain the mean number of using each app. Two items also will be assessed "self-reported number of completed days for each app," and level of comfort with the app "I am comfortable using the app." Participants in Arms 2 & 3 will also complete The System Usability Scale (SUS) at call 1 & 2 and the 3-month follow-up to evaluate the overall usability of and satisfaction with the app (John Brooke, 1986).
- Acceptability. The acceptability will be assessed by 3 items "How satisfied were you with the intervention?", "How likely are you to recommend this intervention to a friend?" and "How useful was the intervention?"
- Feasibility. We will monitor rates of recruitment and effort required (e.g. number of staff hours) as well as the number of screenings conducted, proportion eligible, and proportion who agree to enroll. Feasibility of recruitment will be operationalized as an enrollment rate of 70% or higher (an established standard in the RCT literature). We will also record number of rescheduled, cancelled, and missed assessment visits as well as received visits/calls in each treatment arm to inform estimation of staffing needs and retention protocols for a planned efficacy RCT. Other outcomes are rate of attrition (not having a final visit at the end of treatment), rates of several categories of attrition (mortality, withdrawal from the study, transfer to non-study clinics, loss to follow-up without identifiable cause), and response rates to questionnaires (operationalized as 70% or higher), adherence/compliance rates (operationalized as completing at least 70% of the app's module in arm 2 & 3), and time needed to collect and analyze data.

Clinical Trials Registration #: NCT03999411

Date: 6/29/20

• *Smoking Cessation*. Main Smoking cessation outcome is 7-day point-prevalent abstinence (defined as self-report of not smoking in the past 7-days; not even a puff) confirmed by breath CO cotinine level of < 10 ng/ml at the 3-month follow up. Secondary outcome is the reduction in number of cigarettes smoked per day. Relapse is defined as smoking at least once/week on two consecutive weeks. Adherence to ART. >95% adherence to ART (using VAS).

Participants will receive \$50 for completing the three-month assessment.

As an evaluation of the feasibility of the app-based intervention, we will call participants in Arms 2 & 3 once a week for 3 weeks to ask a brief set of questions about their mindfulness practice and use and opinions of the app. Participants will receive \$5 per each of these 3 calls they complete (for a total of up to \$15). From these two arms, we will randomnly select 6 participants that will be asked to complete daily, instead of weekly calls, for a period of 3 weeks; they will receive \$5 per each call for a total of up to \$105 (\$5 per call x 21 calls).

We will use Google Voice to communicate with participants via text for reminders (ex: appointments scheduled, using the apps on schedule, phone call reminders, follow-up reminders). These texts will not mention "HIV", only that it is part of a research study.

Aim 2. Post-intervention Process Evaluation

After the intervention, in-person semi-structured post-intervention evaluation interviews will be conducted with participants from the "Crave-to-quit + emocha" and "only crave-to-quit" groups to further inform our assessment of acceptability and perceived helpfulness of interventions, and identifying key areas for refining the intervention protocols (e.g., improving access, content, usability). Participants will receive a \$50 incentive for participating. This interview will be audio-recorded and transcribed and may take place the same day of the 3-month follow up visit or on a separate date.

6) Data and Specimen Banking*

7) Data Management*

Participant paper assessments will be stored in a locked filing cabinet in CRB 942. Data from the surveys will be entered into and stored in REDCap, accessed only by approved study personnel. Data will be downloaded and entered into a statistical software program for analysis. Audio files and transcripts from the post-intervention evaluation will be saved in Box and accessed only by approved study personnel.

8) Risks to Subjects*

The risks associated with participating in this study are those related to answering basic questions about demographic characteristics and smoking behaviors. Participants will be

Clinical Trials Registration #: NCT03999411

Date: 6/29/20

assured that their data and any audio recordings will be kept confidential and that they are free to not answer any questions.

9) Potential Benefits to Subjects*

Participants may be able to quit smoking through use of the intervention in the study.

10) Vulnerable Populations*

Those with HIV.

11) **Setting**

The study will take place at the Don Soffer Clinical Research Center, the Infectious Disease Research Unit, and Miami HIV community health centers.

12) Resources Available

The PI of the study, [name], has many years' experience in conducting tobacco control studies. [name] is also specialized in tobacco control. [name], the Director of the UM HIV Research Unit in the Department of Infectious Diseases, has expertise in HIV research, and will assist in coordinating recruitment.

13) Prior Approvals

Letters of Support from Drs. [name] at the UM HIV Registry and [name] from the Behavioral CFAR Core are attached.

14) Recruitment Methods

We are collaborating with Drs. [name] (the Director of the UM HIV Registry) and [name] (Co-I; the Director of the UM HIV Research Unit) to recruit those who were identified as smokers in their database and have agreed to participate in future research (pls. see LOS from Drs. [name] and [name]). We will be provided with a list of potential participants including their names, contact information, smoking status, most recent HIV-1 viral load (VL), and ART regimen history (e.g., time since first starting ART, current prescription). This will include HIV Registry participants who have previously given consent to be contacted for future research studies. Eligible participants will be contacted by phone and invited to participate in the study. Those who are interested will be screened. Those who are eligibility will be scheduled to attend the orientation session. Those who are not eligible, or decline to participate will be encouraged to quit smoking and given a list of available resources. We will additionally recruit participants at HIV community health centers in Miami. The process here will be the same, where interested participants will be screened for eligibility and scheduled for an orientation session.

15) Local Number of Subjects

We will recruit up to 75 participants.

Clinical Trials Registration #: NCT03999411

Date: 6/29/20

16) Confidentiality

All participant data will be stored in a locked cabinet or in REDCap and accessed only by approved study personnel. Their name will be replaced with an ID number on their survey data and a key linking the two will be available only to approved research personnel and only for purposes of contacting them as needed in the study. Their name will not be associated with interview transcripts. Audio files from the interviews and electronic files such as verbal consents will be stored in Box and accessed only by approved study personnel.

17) Provisions to Protect the Privacy Interests of Subjects

Participants can be assured that the personal information they provide will only be seen by approved research staff and they will not be identified in any publication.

18) Consent Process

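### The ART entry rule does not require current ART, and the >95% outcome takes no account of baseline, so the adherence signal mixes improvement with maintenance

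*Protocol*

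**What the plan says.** Protocol section 2 (Objectives) sets out to test the potential efficacy of Crave-to-Quit combined with emocha "to improve ART adherence among PLWHIV smokers". In section 4 (Inclusion and Exclusion Criteria) the only ART condition is "have been prescribed ART medication in the prior 6 months". No inclusion or exclusion criterion asks whether ART is current or how adherent the person is.

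In section 5 (Procedures Involved) the ART outcome is given only as ">95% adherence to ART (using VAS"), under the 3-month assessments and without reference to the entry value.

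The information needed to do better is largely collected already:

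- The registry list includes "ART regimen history (e.g., time since first starting ART, current prescription").
- The baseline assessment records "current ART prescription, 72 VAS for adherence to ART".
- The 3-month visit repeats "All baseline assessments except demographics".

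The orientation-session text in section 5 places the baseline assessment after a video that differs by arm.

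**The concern.** There are two separate gaps.

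**Current ART.** A person whose ART was prescribed five months ago and has since been discontinued meets the criterion. In Arm 3 that person has no doses to film, and in any arm it is unclear what a VAS adherence rating would mean.

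**Baseline level.** The aim is improvement, but the outcome is a level. A participant at 100% at entry and at 100% at 3 months is counted in the same way as one who rose from 60% to 100%.

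The contrast that isolates emocha is Arm 3 versus Arm 2. If many participants enter above 95%, that contrast may look small even when emocha helps those with poor adherence. A high success rate in any arm may also simply reflect who was enrolled. Either reading could mislead the planned larger trial.

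**Working it through.** The protocol states no power, effect size or expected adherence for this outcome, so there is no figure of its own to reproduce.

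**Inputs from the protocol.** Section 15: "We will recruit up to 75 participants". Section 5: "participants will be randomly assigned to one of three treatment arms". The threshold is above 95% on the VAS.

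**Assumptions.** Equal allocation with all 75 recruited and followed, so 75 / 3 = 25 per arm. A share b is above 95% at entry. Among the rest, 25% reach above 95% without emocha and 50% with it, an effect of 25 points.

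**Case 1: nobody above 95% declines in either arm.**

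Success without emocha = b + (1 − b) × 0.25. Success with emocha = b + (1 − b) × 0.50. Difference = (1 − b) × 0.25.

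| b | Able to improve, per arm: 25 × (1 − b) | Without emocha | With emocha | Difference (points) |
|---|---|---|---|---|
| 30% | 17.5 | 47.5% | 65.0% | 17.5 |
| 50% | 12.5 | 62.5% | 75.0% | 12.5 |
| 70% | 7.5 | 77.5% | 85.0% | 7.5 |

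At b = 70% the arm without emocha shows 77.5% success, although only 25% of those able to improve did so. Given no decline, the factor (1 − b) holds for any pair of conversion rates.

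**Case 2: emocha also prevents decline.** Suppose that, of those above 95% at entry, 80% stay there without emocha and 95% with it, a maintenance effect of 15 points (also an assumption).

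Difference = b × 0.15 + (1 − b) × 0.25.

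| b | From maintenance | From improvement | Difference (points) |
|---|---|---|---|
| 30% | 4.5 | 17.5 | 22 |
| 50% | 7.5 | 12.5 | 20 |
| 70% | 10.5 | 7.5 | 18 |

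Most of the shrinkage goes, but at b = 70% more than half of the 18 points comes from maintenance. The single figure cannot show which effect produced it.

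**Precision of a separate report (Case 1 rates).** The 95% half-width is 1.96 × √[(p0(1 − p0) + p1(1 − p1)) / n], where p0 and p1 are the success rates without and with emocha.

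| b | Whole sample, n = 25 per arm | At or below 95% only, n = 25 × (1 − b) per arm |
|---|---|---|
| 30% | 17.5 ± 27.1 | 25 ± 31.0 |
| 50% | 12.5 ± 25.5 | 25 ± 36.7 |
| 70% | 7.5 ± 21.5 | 25 ± 47.3 |

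The separate estimate answers the improvement question, but with a wide interval.

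**The case against.** The strongest reply is that emocha may well help people who enter above 95%. Everyone enrolled is about to try to quit. Protocol section 3 describes cessation as a major stressor and justifies video observation as tracking ART while quitting, and the title speaks of supporting adherence. A 3-month threshold captures prevented loss as well as gain. This stands: a reader might infer that such participants cannot benefit, but the protocol's own rationale points the other way, and the Case 1 figures hold only if nobody declines.

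Second, the baseline VAS is collected and repeated, and baseline adjustment or a subgroup is commonly left to the SAP, which is not at hand. This stands as far as the analysis goes, so it cannot be said that the baseline score will go unused. It does not cover who is enrolled, which the protocol decides.

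Third, a prescription within 6 months is an ordinary proxy for being on ART, and how many would have stopped is unknown. A patient who has lapsed but still has a prescription has the most room to improve, and a VAS near zero is meaningful for that person. This narrows the first gap to people whose ART has been discontinued or whose prescription has ended.

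Fourth, this is a pilot with no power claim, and a larger trial with the same broad entry would need the overall effect for planning. This also stands, and is a reason to keep the whole-sample outcome.

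**Conclusion.** The point holds in a limited form. As written, the criterion admits people no longer on ART, for whom neither the Arm 3 task nor the VAS outcome is well defined. The outcome also does not separate improvement from maintenance, although the objective is improvement.

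The size depends on b, which the protocol does not give. If nobody declines, the effect among those able to improve is multiplied by (1 − b); if few enter above 95%, little is lost. If emocha prevents decline, the loss is smaller, but the overall result is then a mixture.

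Two stronger readings are not supported. One is that the comparison is biased: allocation is random, so both gaps affect the arms alike on average, and what is lost is sensitivity and interpretability of the potential-efficacy signal. The other is that entry should be limited to people at or below 95%: the smoking objective has no need of such a limit, and it would slow recruitment.

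**What to change.** 1. **Entry.** Change the criterion to a current ART prescription at screening. Word it by prescription rather than by intake, so that a poorly adherent person with a live prescription stays eligible. The item is already on the registry list and in the baseline assessment; recruits from community health centres would be asked at screening.
2. **Outcome.** Keep above 95% at 3 months in all randomised participants and adjust it for baseline VAS. Report it separately for those at or below 95% at entry (improvement) and those above 95% (maintenance). Base any statement about improving adherence on the first group.
3. **Timing.** Take the baseline VAS before the arm-specific video, for example at the phone screen, so that the split does not depend on a score given with the arm known.
4. **Entry restriction.** Do not add an adherence ceiling.

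The cost is one changed eligibility phrase, a short addition to the outcome definition, and one question moved to the phone screen, which the verbal consent there would need to cover. People whose prescription has ended would no longer be eligible. The improvement result will rest on fewer people and be imprecise, and should be reported with its interval as an input to planning rather than as a test.
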